(including nesiritide and carperitide), positive inotropic agents and vasopressors, or mechanical support (endotracheal intubation, mechanical ventilation; intra-aortic balloon pump or any ventricular assist device; hemofiltration, ultrafiltration or dialysis), with the exception of IV furosemide (or equivalent), or IV nitrates at a dose of  $\leq 0.1$  mg/kg/hour if the patient has a systolic BP  $>150$  mmHg at screening.

9. Hepatic disease unrelated to HF etiology and as determined by any one of the following: AST and/or ALT values exceeding 3 X ULN and/or bilirubin  $> 1.5$  X ULN at screening, history of hepatic encephalopathy, esophageal varices, or portacaval shunt, diagnosis of cirrhosis, chronic Hepatitis B or chronic Hepatitis C infection by any means (e.g. based on history, clinical findings, laboratory results or imaging)
10. Major surgery, including implantable devices (e.g. ICD, CRT), or major neurologic event including cerebrovascular events, within 30 days prior to screening
11. Any major solid organ transplant recipient or planned/anticipated organ transplant within 1 year.
12. History of malignancy of any organ system (other than localized basal cell carcinoma of the skin), treated or untreated, within the past year with a life expectancy less than 1 year
13. Pregnant or nursing (lactating) women, where pregnancy is defined as the state of a female after conception and until the termination of gestation, confirmed by a positive hCG laboratory test
14. Women of child-bearing potential, defined as all women physiologically capable of becoming pregnant, unless they are using highly effective methods of contraception during dosing of study treatment and for 5 days following the cessation of study treatment. Highly effective contraception methods include:
  - Total abstinence (when this is in line with the preferred and usual lifestyle of the subject). Periodic abstinence (e.g., calendar, ovulation, symptom thermal, post-ovulation methods) and withdrawal are not acceptable methods of contraception
  - Female sterilization (have had surgical bilateral oophorectomy with or without hysterectomy) or tubal ligation at least six weeks before taking study treatment. In case of oophorectomy alone, only when the reproductive status of the woman has been confirmed by follow-up hormone level assessment

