2.1.3 Time window, baseline and post-baseline definitions, and missing data handling

Screening phase (Hour -16): The screening phase is the time period prior to randomization, which should be within 16 hours after presentation. After obtaining written informed consent, the subject will be evaluated for eligibility to participate in to the study.

All references to index hospitalization refer to the initial hospitalization for acute heart failure (AHF).

Baseline (Hour 0/Day 1): The assessments identified in the eCRF as baseline assessments will be used as the baseline reference for all analyses. The baseline date and time will be considered the date and time of initiation of study drug, or randomization if the subject was not treated with study drug. If the value is missing, the last value at screening visit will be used.

Post-baseline phase: The post-baseline phase begins at the time when study drug administration starts (Hour 0/Day 1) and ends with the last study assessment/last follow-up or the death of subject. For subjects who did not receive study drug, the post-baseline phase begins at time of randomization.

Time window: For the scheduled post-baseline visits, time window is not defined; the data will be used as reported in eCRFs (i.e., the actual assessment times will not be used to

[figure not shown]
reclassify the time point at which a measure was taken). The by-visit report will be presented by protocol scheduled visit. Time-to-event analyses will be based on actual date and time as reported when available.

Missing data handling

Missing data handling for efficacy endpoints are discussed in [Section 2.2](#), Efficacy evaluation. In general, missing values of other assessment/measurement will not be imputed unless otherwise specified.

The dates for efficacy endpoint events and AE events should be reported as instructed in eCRFs. If a partially missing date cannot be resolved after data query, the following is the general rule for imputation as necessary only if the calculation is needed (e.g., to calculate time-to-event):

- a) if only the month of the event is known, then the 15th day of this month will be imputed for a missing day in case the month and year are after the month and year of double blind treatment start. If the month and year are equal to the double blind treatment start then the event date will be imputed by the treatment start date.

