2.4.2.2 Clinical chemistry

The following serum chemistry tests will be measured locally at screening and centrally at baseline and post-baseline: sodium, potassium, glucose, blood urea nitrogen (BUN) or urea, AST, ALT, alkaline phosphatase, total bilirubin, and creatinine. In addition, BNP/NT pro-BNP, eGFR and hemoglobinA1c will be measured locally at screening only.

Hematology and clinical chemistry data from central lab will be summarized for safety population by presenting shift tables using extended normal ranges (baseline to most extreme post-baseline value), summary statistics of raw data and change from baseline (means, medians, standard deviations, 1st and 3rd quartiles (Q1 and Q3), and by flagging of notable values in data listings. Shift tables are based on the cross-classification of the number of subjects with clinical laboratory values below (low), within (normal), or above (high) normal ranges for each laboratory test.

The number and percentage of subjects with clinically notable laboratory results after baseline will be presented. Clinically notable laboratory values are defined below.

Table 2-7 Clinically notable laboratory abnormalities for selected tests

Parameter	Criteria (based on a percent change from baseline)
Hematology	
RBC count	>50% increase, >25% decrease
Hemoglobin	>50% increase, >25% decrease
Hematocrit	>50% increase, >25% decrease
WBC count	>100% increase, >50% decrease
Platelet count	>100% increase, >50% decrease
Blood Chemistry	
ALT (SGPT)	defined in Section 2.4.7.1 (liver toxicity)
AST (SGOT)	defined in Section 2.4.7.1 (liver toxicity)
BUN	>100% increase
Creatinine	>100% increase
Total bilirubin (TBL)	defined in Section 2.4.7.1 (liver toxicity)
Alkaline phosphatase (ALP)	defined in Section 2.4.7.1 (liver toxicity)
Potassium	>25% increase, >25% decrease
Calcium	>20% increase, >20% decrease
Uric acid	>100% increase

ALT: alanine aminotransferase; AST: aspartate aminotransferase; ULN: upper limit of normal range

The data from local and central laboratory will be presented separately. All laboratory data from central lab will be listed for each subject. Laboratory values that are outside the normal ranges will be flagged high (H) or low (L). Data from local laboratory will be listed separately by lab.

Creatinine and eGFR

eGFR will be calculated using simplified Modification of Diet in Renal Disease (sMDRD).

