2.4.4 Electrocardiogram (ECG)

The following quantitative variables will be summarized: ventricular rate, PR interval, QRS duration, QT interval, and corrected QT interval (QTc).

The number and percentage of subjects with the following criterion will be presented.

- QT > 500 msec
- QT > 480 msec
- QT > 450 msec
- QT increases from baseline ≥ 30 msec
- QT increases from baseline ≥ 60 msec
- PR > 200 and ≤ 220 msec
- PR > 220 msec
- PR increases from baseline $> 25\%$ (PR > 200 msec)
- QRS > 110 and ≤ 120 msec
- QRS > 120 msec
- QRS changes from baseline $> 25\%$ (QRS > 110 msec)

- Heart rate >100 beats per minute
- Heart rate < 50 beats per minute

QT data will be analyzed for the Fridericia (primary) corrections.

In addition, shift tables comparing baseline ECG results (normal, abnormal, not available, total) with the maximum on-study result (normal, abnormal, not available, total) will be provided for each variable.

A listing of all newly occurring or worsening abnormalities will be provided, as well as a by-subject listing of all quantitative ECG parameters.

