2.4.7.1 Liver toxicity function

The liver toxicity (LFT abnormality) will be identified with the Adverse Event (jaundice and “Drug-related hepatic disorders - severe events only” SMQ AE), and the laboratory parameters mainly AST (aspartate aminotransferase; also known as SGOT), ALT (alanine aminotransferase; also known as SGPT), ALP (alkaline phosphatase) and TBL (total bilirubin; conjugated (direct) and unconjugated (indirect) bilirubin).

The standard SMQ-PT table and odds ratio will be used to provide the number and percentage of subjects with hepatic disorders as mentioned in [Section 2.4.1.2](#), Selected AEs.

The laboratory parameters for liver function will be shown in the laboratory standard tables as discussed in [Section 2.4.2.2](#).

In addition, summary tables will be provided on the number and percentage of subjects who meet the following criteria at post baseline.

Table 2-8 Criteria for evaluating liver toxicity

[figure not shown]
Parameter	Criterion
ALT or AST	ALT or AST > 3xULN ALT or AST > 5xULN ALT or AST > 8xULN ALT or AST > 10xULN
Hy's category	ALT or AST >3x ULN and TBL >1.5x ULN ALT or AST > 3xULN & TBL > 2xULN ALT or AST > 5xULN & TBL > 2xULN ALT or AST > 8xULN & TBL > 2xULN ALT or AST > 10xULN & TBL > 2xULN ALT or AST > 3xULN & TBL > 2xULN & ALP < 2xULN
TBL&ALP	TBL >1.5x ULN and ALP >2x ULN TBL >2x ULN and ALP >2x ULN
Isolated TBL	TBL >1.5x ULN & ALT and AST \leq 3x ULN and ALP \leq 2x ULN TBL >2x ULN & ALT and AST \leq 3x ULN and ALP \leq 2x ULN TBL >3x ULN & ALT/AST \leq 3x ULN and ALP \leq 2x ULN
Isolated ALP	ALP >1.5x ULN & ALT and AST \leq 3x ULN and TBL \leq 1.5x ULN ALP >2x ULN & ALT and AST \leq 3x ULN and TBL \leq 1.5x ULN ALP >3x ULN & ALT and AST \leq 3x ULN and TBL \leq 1.5x ULN ALP >5x ULN & ALT and AST \leq 3x ULN and TBL \leq 1.5x ULN

ALP: alkaline phosphatase; ALT: alanine aminotransferase; AST: aspartate aminotransferase; TBL: total bilirubin; ULN: upper limit of normal.

Plots showing the relationship between TBL and ALT or AST (eDish plot) will also be provided.

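### Minor: SAP Table 2-8 counts liver thresholds met at any time after baseline with no new-onset count beside them, and one two-week stop in protocol Table 14-2 cannot act in a 48-hour infusion

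*SAP*

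**What the plan says.** **Counting rule.** SAP 2.4.7.1 states that "summary tables will be provided on the number and percentage of subjects who meet the following criteria at post baseline". Table 2-8 then gives 19 criteria, all in multiples of ULN; one of the Isolated ALP rows, for example, begins "ALP >2x ULN & ALT and AST". SAP 2.1.3 starts the post-baseline phase when study drug starts, so post-baseline restricts the time of the value and nothing else.

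**Baseline.** The assessment marked as baseline in the eCRF is used. "If the value is missing, the last value at screening visit will be used". Screening chemistry is local; baseline and later chemistry is central (protocol 6.5.3).

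**Other liver summaries.** SAP 2.4.2.2 plans change-from-baseline statistics and shift tables from baseline to the most extreme later value, classing "clinical laboratory values below (low), within (normal), or above (high) normal ranges for each laboratory test". It also plans listings: "All laboratory data from central lab will be listed for each subject". SAP 2.4.1.2 and 2.4.7.1 plan an analysis of hepatic adverse events with odds ratios and 95% confidence intervals, and SAP 2.4.1.1 defines incident events as those starting after study drug. Plots of bilirubin against ALT or AST are planned too.

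**Other tests.** Table 2-7 uses percent change from baseline for hematology, BUN, creatinine, potassium, calcium and uric acid, but refers ALT, AST, bilirubin and ALP to 2.4.7.1. For the ECG, SAP 2.4.4 lists absolute QT limits and also "QT increases from baseline" of at least 30 and at least 60 msec.

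**Eligibility.** Exclusion 9 (protocol 4.2) opens "Hepatic disease unrelated to HF etiology and as determined by any one of the following". Its laboratory limits are AST and/or ALT above 3 x ULN and/or bilirubin above 1.5 x ULN at screening. ALP is not named.

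**Stopping.** For ALT or AST above 5 and up to 8 x ULN, protocol Table 14-2 asks for a repeat test within 48 hours, and for discontinuation if the elevation lasts longer than two weeks. Protocol 5.5.5 caps the time from start to end of infusion at 48 hours.

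**The concern.** Congestion in acute heart failure can itself raise liver tests, and the entry criteria leave room for that. A patient who is above a Table 2-8 threshold before dosing and stays there is counted in the same cell as a patient who crosses it on treatment. The reader wants to know how many patients newly reached each threshold in each arm, and no planned table shows it. Hepatotoxicity is a listed event of interest in SAP Table 2-6, so the contrast between arms should be as clear as the data allow.

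The Table 14-2 clause is a separate matter of protocol wording: an instruction carrying a duration that the treatment period cannot contain.

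**Working it through.** The plan states no figure for this point, so there is nothing to reproduce. The check has three steps.

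**1. Which rows can be met before dosing.** Rows: ALT or AST 4 + Hy's category 6 + TBL and ALP 2 + Isolated TBL 3 + Isolated ALP 4 = 19. The first 15 all require ALT/AST above 3 x ULN or bilirubin above 1.5 x ULN. The last 4 require neither.
- If any value beyond the exclusion 9 limits excludes the patient, whatever its cause, the 4 Isolated ALP rows can still be met at screening.
- If the opening words of exclusion 9 are taken literally, elevation due to heart failure is admitted, and all 19 rows can be met.

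This shows what is possible. It says nothing about how often it occurs.

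**2. Illustration of the dilution.** From the documents: 1,520 / 2 = 760 per arm. Assumed, because the documents give no rates: new onset in 3% (placebo) and 6% (serelaxin) of patients below the threshold at baseline; a share b of each arm above it at baseline; a share s of those still above it afterwards. Then:
- counted proportion = b·s + (1 − b)·p, with p = 0.03 or 0.06
- risk difference = (1 − b) × 3 points, whatever s is
- treatment-emergent count = 760·(1 − b)·p, on a denominator of 760·(1 − b)

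For b = 0.10 and s = 1: placebo 0.10 + 0.90 × 0.03 = 0.127, or 96.5 patients; serelaxin 0.10 + 0.90 × 0.06 = 0.154, or 117.0 patients. The ratio is 1.21 and the difference 2.70 points. The pre-existing part is 2 × 76 / (96.5 + 117.0) = 71%.

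| b | Counts, s = 1 | Ratio, s = 1 | Pre-existing part, s = 1 | Ratio, s = 0.5 | Pre-existing part, s = 0.5 | Difference (points) | Treatment-emergent counts | Denominator per arm |
|---|---|---|---|---|---|---|---|---|
| 0% | 23/46 | 2.00 | 0% | 2.00 | 0% | 3.00 | 23/46 | 760 |
| 2% | 38/60 | 1.60 | 31% | 1.75 | 18% | 2.94 | 22/45 | 745 |
| 5% | 60/81 | 1.36 | 54% | 1.53 | 37% | 2.85 | 22/43 | 722 |
| 10% | 97/117 | 1.21 | 71% | 1.35 | 55% | 2.70 | 21/41 | 684 |
| 15% | 133/153 | 1.15 | 80% | 1.25 | 66% | 2.55 | 19/39 | 646 |

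By construction the treatment-emergent comparison keeps a ratio of 2.00 and a difference of 3.00 points. The absolute counts lose a good deal on the ratio scale and little on the difference scale. The SAP plans numbers and percentages for Table 2-8, not ratios, so the ratio column only describes what a reader comparing two percentages would see.

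**3. Timing of the two-week clause.** Two weeks = 14 × 24 = 336 h, seven times the 48 h cap. For an elevation present at Hour 0, the condition is met no earlier than 336 − 48 = 288 h after the cap. For one first seen at the first scheduled post-baseline chemistry (Hour 24, protocol Table 6-1), it is met no earlier than Hour 24 + 336 = 360, which is 360 − 48 = 312 h after the cap. The clause can never stop an infusion. The repeat-test window that opens at Hour 24 closes at Hour 72, also after the infusion has ended.

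**The case against.** The strongest reply is that Table 2-8 contains no error. Absolute counts by ULN multiple are a deliberate choice, and no document promises a treatment-emergent count. The QT rows show a different choice for a different test, not a contradiction. This stands: the point is an improvement, not a correction.

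The second reply is that new-onset liver findings are already analyzed. A reader might infer from Table 2-8 alone that liver safety has no baseline-referenced summary; the documents do not support that. Incident hepatic adverse events are compared with odds ratios, and protocol 7.1 makes a laboratory abnormality an adverse event if it is symptomatic, clinically significant or needs therapy. The shift tables show moves from normal to high. What they do not show, as described, is movement between ULN multiples: a patient going from 1.5 to 6 x ULN is high at both times. The SAP mentions extended normal ranges but does not define them. The remaining gap is therefore new-onset counts at the Table 2-8 thresholds, which a reader would have to rebuild from listings.

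The third reply is that the magnitude is assumed throughout. That also stands.

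On the two-week clause, a reader might infer that patients between 5 and 8 x ULN are unprotected or that sites have no guidance. Neither follows. ALT or AST above 5 x ULN is a liver event in protocol Table 14-1, and 7.3 directs discontinuation where appropriate. Sections 5.5.5 and 5.5.9 allow or require a stop on safety grounds, and Table 14-2 keeps immediate stops for potential Hy's Law cases, values above 8 x ULN, values above 3 x ULN with symptoms, and jaundice. Nor can anything be concluded about how fast results reach sites, since 6.5.3 leaves reporting details to the laboratory manual.

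**Conclusion.** Both points hold at minor severity.

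Table 2-8 mixes pre-existing with new abnormalities, and no planned table separates them at its thresholds. The size is unknown: it depends on baseline shares and persistence that the documents do not give and that will differ by row. It is tempting to read this as a biased safety comparison. It is not: randomization balances baseline elevation on average, so the effect is dilution without a direction, and no hypothesis test, alpha or sample size depends on these tables. How many rows are exposed depends on how exclusion 9 was applied: 4 of 19 on the strict reading, all 19 on the literal one.

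The two-week clause is certain, because it follows from the protocol's own durations. It is inert wording, not a missing protection.

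**What to change.** **SAP 2.4.7.1.** Keep the absolute counts. For each Table 2-8 criterion add a treatment-emergent count: criterion not met at baseline and met after the start of study drug, with patients not meeting it at baseline as the denominator. Add a shift table from baseline to worst post-baseline value by ULN multiple. Flag patients whose baseline is a local screening value.

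The cost is one programming condition and one extra table on data already collected. The downsides are denominators that differ by row, some baselines from a local laboratory compared with central values, and fewer patients in the new rows if baseline elevation is common (in the illustration, placebo falls from 97 to 21 at a 10% share). That last point is why the absolute counts should stay.

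**Protocol Table 14-2.** For ALT or AST above 5 and up to 8 x ULN, replace the two-week condition with an action possible during infusion and in line with 7.3, such as the investigator deciding on discontinuation when the result is reported. Otherwise delete it. The choice is clinical and belongs to the sponsor's safety team. The cost is a wording change in Appendix 2.

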2.4.7.2 Liver events

[figure not shown]
For subjects who are identified with a liver event, additional information will be collected as pre-printed in the following eCRFs:

2.5 Interim analysis

There will be no formal efficacy interim analysis.

However to monitor subject safety data on a regular basis during the course of the study, an external independent data monitoring committee (DMC) has been established and will review safety data two times a year as planned in the DMC charter. DMC may request additional safety data reviews as needed. Such safety data reviews do not inflate the type I error for the primary efficacy hypothesis testing and thus require no multiplicity adjustments.

2.6 Other topics

2.6.1 Resource utilization

Summary statistics on hospital length of stay (days) for the index hospitalization and length of ICU/CCU stay for the index and subsequent hospitalizations, as well as procedures rendered during these hospitalizations will be provided by treatment group for FAS.

2.6.2 Health-related Quality of Life

Health related quality of life assessments will not be collected in this study.

2.6.3 Immunogenicity

Anti-serelaxin antibodies will be measured in serum samples collected at the Day 60 time point. To account for individual variability in background of each subject and to check for endogenous interference and/or pre-existing anti-serelaxin antibodies, anti-serelaxin antibodies will also be measured at baseline. The analysis will be done for all subjects who received any study treatment and who had an anti-serelaxin antibody measurement performed.

Results of the anti-serelaxin antibody assays (including anti-serelaxin antibody positive/negative, titer, and neutralizing antibody positive/negative) will be listed by treatment group, subject and sampling time. Incidence rate of positive anti-serelaxin antibodies and neutralizing antibodies will be computed and summarized by treatment group and sampling time.

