### **6.6.3 Immunogenicity**

#### **Immunogenicity blood collection and processing**

Blood samples for immunogenicity will be taken at baseline and on Day 60. They will be taken by either direct venipuncture or an indwelling cannula inserted in a forearm vein contra-lateral to the site of infusion. If an indwelling cannula is used, a 0.5 mL discard will be taken before the immunogenicity sample in case the indwelling cannula was flushed with saline. Serum separator tubes will be used to collect serum for the evaluation of anti-serelaxin antibodies.

For assessment of immunogenicity (anti-serelaxin antibody), approximately 3 mL blood will be drawn into a serum separator tube. Instructions regarding the sample collection and handling including clotting time, centrifuge temperature and duration, storage and shipment are described in the Laboratory Manual.

All samples will be given a unique sample number (as listed in [Appendix 6](#)). The first aliquots should be sent to the bioanalytical center on dry ice, while the back-up aliquots should be sent to the same address after assurance that the first aliquots arrived in good condition and whenever possible together with the next shipment of first aliquots. For detailed instructions on labeling and shipment of samples, please refer to the Laboratory Manual.

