### **9.5.6 Immunogenicity**

Anti-serelaxin antibodies will be measured in serum samples collected at the Day 60 time point. To account for individual variability in background of each subject and to check for endogenous interference and/or pre-existing anti-serelaxin antibodies, anti-serelaxin antibodies will also be measured at baseline. Frequencies and percentages will be computed for occurrence of anti-RLX030 antibodies at each time point. Listings for subjects with a

positive screening result at any time point will include subject number, time point, immunodepletion result, titer, and neutralizing antibody result.

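### The Day 60 antibody 'incidence' is positivity at a time point, not conditioned on the patient's own baseline result, so persistent pre-existing positives count as incident and titer boosts are not summarised

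*SAP*

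**What the plan says.** Protocol 6.6.3 sets two sampling times: "Blood samples for immunogenicity will be taken at baseline and on Day 60". A positive is a screening signal confirmed by immunodepletion. Confirmed positives are then titrated and tested for neutralisation.

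Both analysis sections give the same reason for the baseline sample. In SAP 2.6.3 it reads: "To account for individual variability in background of each subject and to check for endogenous interference and/or pre-existing anti-serelaxin antibodies".

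The planned summaries are:
- SAP 2.6.3: "Incidence rate of positive anti-serelaxin antibodies and neutralizing antibodies will be computed and summarized by treatment group and sampling time".
- Protocol 9.5.6: "Frequencies and percentages will be computed for occurrence of anti-RLX030 antibodies at each time point".

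The SAP analysis set is: "The analysis will be done for all subjects who received any study treatment and who had an anti-serelaxin antibody measurement performed". It does not require a paired sample or a negative baseline.

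In the SAP, assay results (positive or negative, titer, neutralising status) "will be listed by treatment group, subject and sampling time". The protocol's listing is narrower. It covers only subjects with a positive screen, and listings for those with a "positive screening result at any time point will include subject number, time point, immunodepletion result, titer, and neutralizing antibody result".

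Neither section defines a treatment-induced or treatment-boosted antibody, a baseline-by-Day 60 cross-tabulation or a baseline-negative denominator.

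**The concern.** The reason given for the baseline sample works within the patient: it allows for each person's own background. The summary works on the margins: one percentage at baseline and another at Day 60. Three things follow.

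- A patient with pre-existing, unchanged reactivity is counted in a Day 60 figure that the SAP calls incidence.
- A baseline-positive patient whose titer rises after the infusion looks the same in the summary as one whose titer does not, although titers are measured.
- The two percentages can rest on different patients, because one antibody measurement is enough to enter the analysis and some patients will die or miss the Day 60 visit.

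The useful safety quantity is the proportion of patients in whom the infusion induced or boosted antibodies. The planned tables do not report it, and the two marginal rows cannot recover it. At stake is a figure that could be quoted as the incidence of anti-serelaxin antibodies when part of it was present before dosing.

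**Working it through.** The documents state no antibody rate, so there is no figure of the plan to reproduce. The check has a textual part and an illustration on assumed rates.

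**1. Can the two marginal rows give the number of new positives?** Take 760 patients in an arm (1,520 randomised 1:1, SAP 2.7), all with both samples, and assume 2% positive at each time: 760 × 0.02 = 15.2. If every baseline positive persists, there are 0 new positives. If every baseline positive reverts, there are about 15. Both cases give the same planned table, so the rows do not identify the quantity.

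**2. How far does the planned Day 60 rate differ from the newly positive rate?** Let b be the baseline positivity, assumed to persist to Day 60, and t the rate of new positivity among baseline-negative patients.

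- Planned Day 60 rate = b + (1 − b)t
- Newly positive, over all paired patients = (1 − b)t
- Share of Day 60 positives that were pre-existing = b / [b + (1 − b)t]

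All values of b and t are assumptions. Counts are per 760 patients.

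| b | t | Planned Day 60 rate (n) | Newly positive (n) | Pre-existing share |
|---|---|---|---|---|
| 0 | 1% | 1.00% (7.6) | 1.00% (7.6) | 0% |
| 0.5% | 1% | 1.50% (11.4) | 1.00% (7.6) | 33% |
| 1% | 0.5% | 1.50% (11.4) | 0.50% (3.8) | 67% |
| 2% | 1% | 2.98% (22.6) | 0.98% (7.4) | 67% |
| 5% | 0.5% | 5.48% (41.6) | 0.48% (3.6) | 91% |
| 5% | 2% | 6.90% (52.4) | 1.90% (14.4) | 72% |

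The last row in full: 0.05 + 0.95 × 0.02 = 0.069, against 0.95 × 0.02 = 0.019. Over baseline-negative patients only, the rate would be t itself, 2.0%. For b from 0.5% to 5% and t from 0.2% to 2%, the planned rate runs from 0.70% to 6.90%, and 20% to 96% of the Day 60 positives are pre-existing. At b = 0 the two measures agree among patients with both samples.

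**3. Is the comparison with placebo biased?** Take b = 5% in both arms, t = 2% on serelaxin and 0.5% on placebo (assumed).

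- Planned rates: 0.069 − (0.05 + 0.95 × 0.005) = 0.069 − 0.05475 = 0.01425
- Newly positive rates: 0.019 − 0.95 × 0.005 = 0.019 − 0.00475 = 0.01425

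The expected differences are identical, both (1 − b)(t₁ − t₀). The background cancels.

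**4. What happens to precision?** Assume 700 evaluable patients per arm and a Wald 95% interval for the same contrast.

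- Planned rates: 1.96 × √[(0.069 × 0.931 + 0.05475 × 0.94525)/700] = 0.025, or ±2.5 points
- Newly positive rates: 1.96 × √[(0.019 × 0.981 + 0.00475 × 0.99525)/700] = 0.011, or ±1.1 points

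With b = 2% the planned-rate half-width is 1.85 points, and with b = 10% it is 3.3. The newly positive half-width stays at 1.1 to 1.2. These figures show direction and order of size only, because the plan specifies no interval or test for antibodies.

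**The case against.** The strongest reply is that nothing is lost from the database. The SAP shows baseline positivity by arm in its own row, which serves the stated check for pre-existing antibodies. It also lists each analysed patient's result, titer and neutralising status at both times, so seroconversion can be read off. The placebo arm shows the background at Day 60. The exclusion of earlier serelaxin participants removes one source of baseline positivity, though not natural antibodies. Immunogenicity is not a numbered objective, and clinical hypersensitivity events are summarised separately with odds ratios in SAP 2.4.1.2.

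Much of this stands, and it rules out several stronger readings that a reader might infer:

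- *That the baseline sample goes unused.* It is tabulated and listed. It is only not used to condition the Day 60 rate.
- *That the figures are bare screening reactivity.* Protocol 6.6.3 requires confirmation by immunodepletion.
- *That pre-existing antibodies bias the arm comparison.* Under randomisation they do not in expectation, as the check shows.
- *That the protocol declares the immunogenicity of a single infusion uncharacterised.* Protocol 3.6 says this of repeated intravenous dosing, as the reason for excluding earlier participants.
- *That the precision loss is known to be large.* Every rate is assumed. It shrinks as background falls and disappears at zero.

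The reply does not repair the summary. A listing is not an analysis. Without a rule fixed beforehand, what counts as a new or boosted response would be decided after the results are seen. The choice of a titer-rise threshold is the most open to this.

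**Conclusion.** The point holds in limited form. The planned Day 60 rate does not deliver the within-patient allowance for background that both documents give as a reason for the baseline sample. Each within-arm rate is a prevalence labelled as incidence. It overstates new positivity by exactly the persistent background, and titer boosts go unsummarised. The arm difference is unbiased in expectation but less precise than it need be.

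The size cannot be set from the documents. It is nil if background positivity is zero, and 5 percentage points in the 5% background example. It rests on two assumptions: that baseline positivity persists to Day 60, and that it is equal across arms.

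This is a descriptive safety summary. It does not touch alpha, power, sample size or any efficacy endpoint. The change is worth making because it is cheap and the data are already collected.

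**What to change.** In SAP 2.6.3, with matching wording in protocol 9.5.6:

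1. Make treatment-emergent antibody status by arm the main summary, among treated patients with both samples. Define it as induced (negative at baseline, confirmed positive at Day 60) or boosted (positive at baseline, with a titer rise above a threshold). The documents give no threshold, so set it from assay variability before unblinding.
2. Report the induced rate over baseline-negative patients as well, and state each denominator.
3. Add a baseline-by-Day 60 shift table by arm, and neutralising status for treatment-emergent patients.
4. Give the arm difference with a 95% CI by a method suited to low counts. In the illustration the placebo arm has only 700 × 0.00475 ≈ 3.3 expected new positives, too few for a Wald interval.
5. Keep the per-time-point table as secondary, call it prevalence, and show the number tested at each time.

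The cost is SAP and protocol wording, one derived variable and one table. Samples, titers and neutralising results are already planned. The downside is selection: patients without a paired sample, including those who die or miss Day 60, leave the main rate. Report their number by arm, and keep the prevalence table so that their available results are still shown.
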